5.2 Handling of Study Interventions

Prior to recruitment, the investigators will meet with community members and peer mentors to discuss adaptations to the intervention protocol, language, and materials to optimize the delivery of the intervention for this study population. Also prior to recruitment, the occupational therapists and peer-mentors at each site will undergo training in intervention principles and standardized procedures. All intervention procedures will be documented using standardized forms available via tablet, and uploaded to REDCap. During the study, the occupational therapists and peer mentors will participate in weekly calls to discuss the implementation of the intervention and assess the need for adaptation. Refer to the intervention manual for specific procedures.

5.3 Concomitant Interventions

5.3.1 Allowed Interventions

All concurrent treatments and services will be permitted, with the exception of concurrent rehabilitation services.

5.3.2 Required Interventions

No interventions beyond ENGAGE are required.

5.3.3 Prohibited Interventions

People receiving concurrent occupational, physical, and speech language pathology rehabilitation services will be excluded from the study.

5.4 Adherence Assessment

Participant adherence will be indicated through attendance at ENGAGE sessions

(90%, 10 of 12 sessions). This will serve as one measure of feasibility. Therapist and peer-mentor adherence, or fidelity to standardized intervention principles, will be assessed using a fidelity checklist in combination with video recordings and session documentation. Refer to the intervention manual for specific procedures.

6. STUDY PROCEDURES

6.1 Schedule of Evaluations

Assessment	Screening: (Day -14 to -1)	Pre- Intervention (Day -14 to -1)	Intervention Sessions (Day 0 to 42)	Post- Intervention (Day 43 to 57)
Referral Log				
Informed Consent				
Screening Assessments	X			
Screening Checklist	X			
Participant Characteristics		X		
Comorbidity Questionnaire		X		
Cognitive Assessment		X		
Social Support Survey		X		
Ability to Participate		X		
Satisfaction with Participation		X		X
Social Isolation		X		X
Global Health		X		X
Community Participation		X		X
Participation Activation		X		X
Participation Self-Efficacy		X		X
Patient Activation		X		X
Chronic Disease Self-Efficacy		X		X
Sedentary Behavior		X		X
Physical Activity Scale		X		X
ActivPal		X		X
Intervention Record			X	

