1.2 Secondary Objectives

The secondary objective of this study is to describe intervention response among

participants at each site, indicated by pre-post change in PROMIS Ability to Participate in Social Roles and Activities. We will also explore changes in satisfaction with participation (PROMIS Satisfaction with Participation in Social Roles and Activities), physical activity (step count/day), sedentary behavior (sitting time/day), social (PROMIS Social Isolation), and perceived health (PROMIS-29) to inform future studies.

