6.2.2 Pre-Intervention Assessment

The pre-intervention assessment will be administered by trained evaluators and will take 1.5 hours.

- The Participant Characteristics Form will record age, sex, race, ethnicity, education, vocational status, residential status, social support, stroke characteristics, and stroke chronicity.
- The Self-Administered Comorbidity Questionnaire is a participant-reported measure of comorbidities. Participants are asked to report on the presence or absence of specific chronic diseases, if they receive treatment for the disease, and if the disease interferes with their daily life activities.
- The Montreal Cognitive Assessment is brief, standardized measure of cognitive function. Participants are asked to complete a series of cognitive tasks assessing attention, memory, visuospatial function, and selected executive function domains, and their performance is scored by a trained assessor.
- The Medical Outcomes Survey Social Support Survey is a brief questionnaire that assesses companionship, assistance and support from others.

- The PROMIS Ability to Participate in Social Roles and Activities 8-item short form will be the primary measure of community participation. The measure assesses difficulty participating in social roles and activities (1=always difficult, 5=never difficult).
- The PROMIS Satisfaction with Social Roles and Activities 8-item short form will be used to assess satisfaction with community participation (1=always satisfied, 5=never satisfied).
- The PROMIS Social Isolation 8-item short form will be used to assess perceptions of social isolation (1=never, 5=always).
- The PROMIS Global Health 43-item short form will be used to assess perceived global health (1=excellent health, 5=poor health).
- The Community Participation Indicators Scale is a detailed questionnaire that assesses the frequency of community participation activities, satisfaction, and degree of enfranchisement (belongingness) that individuals with stroke-related disability have with respect to community participation.
- The Community Participation Activation Scale is a brief questionnaire that assesses the active role that people with stroke-related disabilities take in engaging in community participation.
- The Participation Self-Efficacy Scale assesses confidence in understanding and managing one's community participation.

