- The Chronic Disease Self-Efficacy Scale assesses confidence in understanding and managing one's health condition and associated symptoms.
- The Patient Activation Scale assesses the active role that people with take in managing their health and symptoms.
- The Sedentary Behavior Questionnaire asks participants to report time spent in 9 specific sedentary behaviors during a typical weekday and weekend. This assessment demonstrates validity and reliability for measuring sedentary behavior in the adult population.
- The Physical Activity Scale for Individuals with Physical Disabilities will measure self-reported physical activity. This questionnaire asks participants to report time spent in 13 types of physical activity over the past 7 days.
- ActivPAL(TM) monitors will be used to assess sedentary behavior and step count over 7 days. The ActivPAL is a small, lightweight monitor that quantifies time spent in sitting, reclined, standing, and stepping. The participant will be provided the "ActivPAL Guide" as a reference guide. We will follow a 24-hour wear protocol in which the participants will wear the device on their thigh for 7 days. A trained assessor will train the participant on appropriate care and use of the device. The ActivPAL will be waterproofed and fastened to the individual's thigh using a non-latex, gentle adhesive (Tegaderm). Prior to adhering the device, the assessor will conduct a gross sensation tactile localization screen to detect impairment in sensation on the participant's anterior thigh. The assessor will ask the participant to close their eyes and will lightly touch the participant's anterior thigh in the region where the ActivPAL will be positioned (anterior, upper half). He/she will ask the participant to indicate when and where the researcher touched. If impaired gross sensation is detected, or the participant reports sensitivity to adhesives, alternative strategies for positioning the device and alternate wear

schedules (such as removing the device during non-waking hours or wearing the device for fewer than 7 days) will be identified. Participants will also be asked to record their bedtime and waking time in the "ActivPAL Diary". Sedentary bouts, sedentary breaks, and steps per day will be assessed using the ActivPAL monitor.

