6.2.4 Post-Intervention Assessment

The post-intervention assessment will be administered by trained independent evaluators and will take 1 hour.

- PROMIS Ability to Participate in Social Roles and Activities
- PROMIS Satisfaction with Social Roles and Activities
- PROMIS Social Isolation
- PROMIS Global Health
- Community Participation Indicators Scale.
- Community Participation Activation Scale
- Participation Self-Efficacy Scale
- Chronic Disease Self-Efficacy Scale
- Patient Activation Scale
- Sedentary Behavior Questionnaire
- Physical Activity Scale for Individuals with Physical Disabilities
- ActivPAL(TM) (7 day wear)
- Client Satisfaction Questionnaire

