9.5 Outcomes

9.5.1 Primary Outcome

Feasibility will be indicated by >90% of target enrollment, >90% retention, and >90% intervention fidelity at each site; acceptability will be indicated by >90% participant satisfaction at each site; and safety will be indicated by <3% participants with a reportable event (i.e., injurious fall) at each site, and by phase.

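### Do gaps in the 6.1 Schedule of Evaluations put the satisfaction questionnaire and the main participation score at risk?

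*Combined protocol and SAP*

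**What the plan says.** Section 6.1 sets out a table of 21 rows and four time columns, the last headed "Post- Intervention (Day 43 to 57". No row is labelled for the Client Satisfaction Questionnaire. The row "Ability to Participate" carries a mark at pre-intervention only, as the table reads here.

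Section 6.2.4 lists the post-intervention instruments in words. Its first entry is "PROMIS Ability to Participate in Social Roles and Activities" and its last is "Client Satisfaction Questionnaire".

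Two outcomes depend on these entries:

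- **Acceptability.** Section 9.5.1 (and 1.1 in the same terms) states that "acceptability will be indicated by >90% participant satisfaction at each site". Neither section names the instrument.
- **Intervention response.** Section 1.2 defines it as "indicated by pre-post change in PROMIS Ability to Participate in Social Roles and Activities". Section 6.2.2 says that this short form "will be the primary measure of community participation".

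**The concern.** A schedule of evaluations is the page that site staff tend to keep at hand, and here it disagrees with the text on what is collected at the final visit. The instruments affected are not peripheral. Satisfaction is one of five primary benchmarks (enrolment, retention, fidelity, satisfaction, safety), and the Client Satisfaction Questionnaire is named only once in the documents. Ability to Participate is the lead participation measure, and its change score needs a value after the intervention.

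If a site ran the visit from the table alone, it would have no questionnaire data for the acceptability benchmark. If the blank cell is also in the source table, it would have no change score for the secondary objective. The plan describes no later assessment at which either could be recovered, and the study spans three sites and two delivery phases.

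**Working it through.** The plan states no figure on this point, so the check is a row-by-row comparison of 6.1 with the lists in 6.2.2 and 6.2.4.

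**Counts**

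| Item | Count |
|---|---|
| Rows in 6.1 | 21 |
| Marks in 6.1: screening / pre / sessions / post | 2 / 16 / 1 / 11 |
| Rows in 6.1 with no mark (Referral Log, Informed Consent) | 2 |
| Instruments listed in 6.2.2 | 16 |
| Instruments listed in 6.2.4 | 13 |
| Instruments in both 6.2.2 and 6.2.4 | 12 |

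Four instruments in 6.2.2 are baseline only (participant characteristics, comorbidity, cognition, social support), so 16 − 4 = 12 are repeated. The questionnaire is added after the intervention, so 12 + 1 = 13.

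**Pre-intervention.** All 16 instruments in 6.2.2 have a marked row in 6.1. There is no discrepancy.

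**Post-intervention.** 13 − 11 = 2 instruments are unmatched.

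1. *Client Satisfaction Questionnaire.* The row itself is absent, so a misplaced mark cannot explain it. The Satisfaction with Participation row is not a substitute: it corresponds to the PROMIS satisfaction form and is marked at both visits.
2. *Ability to Participate.* The row is present and the post-intervention cell is empty. Of the 12 repeated instruments, 11 carry both marks and this one does not. If the mark was lost when the PDF was converted, 13 − 12 = 1 instrument remains unmatched.

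**How far the table can be trusted as a literal instruction.** The Informed Consent row has no mark in any column, yet 11.2 requires consent from every participant. Nobody would read that blank as permission to skip consent, and the Ability to Participate blank deserves the same caution. Nor does 6.1 give every instrument its own row: the four screening entries in 6.2.1 are grouped under Screening Assessments, and the fidelity checklist in 5.4, which feeds another primary benchmark, has no separate row.

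**What the rest of the plan requires.** Section 6.2.4 lists both instruments at post-intervention. For Ability to Participate, 1.2 requires a value at both visits, and 9.5.2 and 9.6 analyse within-participant change in community participation. No section says that 6.1 overrides 6.2.4.

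**Effect on figures.** The power statement in 9.2 depends on 60 participants, d = 0.37 and α = 0.05. No table entry enters it. The analyses in 9.5.2 and 9.6 are the same whether or not the table is tidied.

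**The case for a change.** The best case for acting is that two parts of one protocol disagree about a visit that cannot be repeated, and that the remedy costs one row and perhaps one mark, with no added burden on participants. The outcome instruments in 6.1 otherwise follow one row per instrument, so grouping does not readily explain the missing questionnaire row. The 11 rows directly below Ability to Participate all kept their post-intervention marks, and its blank falls just where the baseline-only rows end, which is a plausible place for an author to slip.

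Much of this stands. The missing row is a true inconsistency, and the blank cell is worth a glance at the source table. What does not stand is the step from there to a risk for the results. Nothing in the documents shows that staff or data forms follow 6.1 in preference to 6.2.4. Data collection is reviewed weekly by the Executive Committee and REDCap is reviewed on a schedule (10.3.3), while assessment staff are monitored monthly (10.3.1). These checks might catch an omission, although the plan does not say that they compare forms with 6.2.4. The link from the questionnaire to the satisfaction benchmark is also an inference from its title. It is a reasonable one, but how that benchmark is defined is a separate question from a missing table row.

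**Conclusion.** No change to the plan follows. The omission of the Client Satisfaction Questionnaire from 6.1 is a clerical slip. The blank for Ability to Participate is at most a second slip and may be only a conversion loss. The size is one or two table entries out of 13 post-intervention instruments, with no effect on any stated number, procedure or analysis.

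The conclusion rests on two assumptions: that sites and the REDCap forms follow the explicit list in 6.2.4, and that the questionnaire is the intended source for the satisfaction benchmark. The first is the natural reading, because 6.2.4 is the plan's description of that visit and agrees with the objectives. The second affects how much the missing row would matter, but not whether the questionnaire is planned. Evidence that a site's forms had been built from 6.1 alone would change this view, and the documents contain none.

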6.2 Description of Evaluations

6.2.1 Screening Assessment

The screening assessment will be administered by trained evaluators and will take 1 hour.

- The National Institutes of Health Stroke Scale is a valid and reliable scale to assess neurological impairment associated with stroke. Items test alertness, orientation, command following, eye and limb movements, vision, language and sensory perception.
- The Activity Card Sort is a valid and reliable assessment of community participation.
- The Boston Diagnostic Aphasia Examination severity scale assesses aphasia impairment severity in three domains: comprehension, expression, and fluency.
- The PRIME-MD with Mini-Neuropsychiatric Interview module assesses presence of mood disorders.

N. B. As part of the assessment of mood, we are including items to address risk of suicidality, a potential risk associated with depression. This action was advised by a physician co-investigator and geriatric neuropsychiatrist [name], who advises all assessments of depression including these items. If in the course of assessment it is determined that an individual has either major depressive disorder or suicidality, we will 1) refer the participant to local services (in Pittsburgh, the RESOLVE Crisis Network, a 24 hour service that directs individuals with major depressive disorder and/or suicidality to immediate care), 2) notify the contact person identified by the participant, and 3) notify the treating physician on service at the time of referral. We will document these actions in the study records. This 3-step plan has been effective when we encountered major depressive disorder in our previous studies with this population (over the last 10 years).

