1. STUDY OBJECTIVES

1.1 Primary Objective

The primary objective of this study is to examine the feasibility, acceptability, and safety of a multi-site, multi-phase implementation of ENGAGE to address community participation among adults with stroke-related disability and low income. We will partner with Washington University Community Research Fellows and the University of Pittsburgh Community PARTners to adapt and implement the intervention to address the needs of people with mild to moderate stroke-related disability and low income who live in Pittsburgh, St. Louis, and Chicago. We will clarify and describe the specific adaptations necessary to support this population. We will test this intervention through in-person and remote delivery methods. Feasibility will be indicated by >90% of target enrollment, >90% retention, and >90% intervention fidelity at each site; acceptability will be indicated by >90% participant satisfaction at each site; and safety will be indicated by <3% participants with a reportable event (i.e., injurious fall) at each site.

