The self-management training will be administered by an occupational therapist and a peer-mentor in group sessions (social learning). Individual application of the self-management training content will be facilitated with guided skill development principles. The intervention will be 12 two-hour sessions, offered 2 times per week for 6 weeks, based on previous intervention dosing studies. There are limited known and potential risks because the intervention focuses on doing routine daily activities in the home and the community, as would normally be encountered in the course of everyday life. However, there is a minimal risk of frustration fatigue, fall, or injury that may result from increasing physical and social activity levels over the course of time. These risks will be minimized through supervision of licensed occupational therapists.

ADDENDUM: With the onset of the pandemic, we developed methods to deliver this intervention program remotely. People with stroke-related disability, particularly those in low income communities, face unique problems in the home and the community during pandemic conditions. We decided to add a second phase of the study, delivering the intervention remotely, to address these needs, and to compare metrics across phases (in person, remote).

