3. STUDY DESIGN

This is a multi-site, multi-phase single-arm community-based clinical trial examining the feasibility, acceptability, safety, and variation in changes in community participation attributed to ENGAGE among community-dwelling adults with mild to moderate stroke-related disability and low income. The 6 week intervention (12 two-hour sessions, 2 times per week) intervention will be delivered in community-based settings (in person) or in the home (remote), and assessments will be delivered in the home or community-based settings (in person) or via teleconference (remote). Assessments will be administered by independent evaluators at each site, and all data will be collected electronically and stored in REDCap, a cloud-based data management system accessible to all investigators at all sites.

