7. SAFETY ASSESSMENTS

7.1 Adverse Events

Given the benign nature of the intervention and assessment procedures, we anticipate minimal to no adverse events. Nonetheless we will monitor physical safety of participants during the intervention period, to assess the potential for adverse events.

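### The response to suicidality in section 6.2.1 has no location check for teleconference screens and, in either mode, no rule to stay until a crisis service has taken over

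*Combined protocol and SAP*

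**What the plan says.** Section 6.2.1 includes suicidality items in the mood assessment at screening. The response is triggered when "it is determined that an individual has either major depressive disorder or suicidality", so both findings lead to the same three steps:

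1. Refer to local services. The example given is "in Pittsburgh, the RESOLVE Crisis Network, a 24 hour service that directs individuals" with either condition to immediate care.
2. Notify the contact person whom the participant has identified.
3. "notify the treating physician on service at the time of referral".

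The actions are then documented. The section adds that the plan worked in the investigators' earlier studies when major depressive disorder was found.

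On who does this and for how long, 6.2.1 says: "The screening assessment will be administered by trained evaluators and will take 1 hour". On mode, section 3 says that "assessments will be delivered in the home or community-based settings (in person) or via teleconference (remote"). Section 2.2 gives the origin of the remote phase: "With the onset of the pandemic, we developed methods to deliver this intervention program remotely". On place, section 1.1 describes participants "who live in Pittsburgh, St. Louis, and Chicago".

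**The concern.** Suicidality is the most urgent result this screen can give. The response to it is written as referral and notification, with nothing that depends on whether the evaluator is in the room or on a screen.

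Two things are missing. In a teleconference, sending help or choosing the right local service requires knowing where the person is at that moment, and no step asks. In both modes, the evaluator can refer, notify, document and end the session without confirming that anyone has taken over.

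The screening visit may also be the study's last contact with the person. Current major depressive disorder is an exclusion under section 4.2, and the documents describe no later safety contact for people screened out.

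**Working it through.** The plan states no figure to reproduce. The check is a reading of the relevant sections side by side, a count, and one small sum for the cost.

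**Does the remote mode reach the mood items?** Section 3 speaks of assessments in general and makes no exception for screening. The mood items are listed under screening in 6.2.1 and do not reappear in the post-intervention list in 6.2.4. So the point concerns the screening visit, including any held by teleconference.

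**What do the three steps cover?**

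| Element | Step 1 (refer) | Step 2 (contact person) | Step 3 (physician) | Count |
|---|---|---|---|---|
| Confirms current location | no | no | no | 0 of 3 |
| Puts a call-back number in front of the evaluator | no | no | no | 0 of 3 |
| Requires staying until someone has taken over | no | no | no | 0 of 3 |

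A crisis service is named for 1 of the 3 cities (Pittsburgh).

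**Does another section supply the missing elements?**

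- Section 4.3 has the team follow up each interested person with a telephone call before consent. A number will therefore usually exist. The section does not say that the evaluator has it to hand during the screen, and a number does not give a location.
- Section 7.1 says "we will monitor physical safety of participants during the intervention period". That is physical safety, and the period begins after screening.
- Section 7.3 provides a weekly committee review, which is too slow for an acute finding.
- The references to the intervention manual in sections 5.1, 5.2 and 5.4 concern delivery of and adherence to the intervention, not screening.

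So current location and live handover are not covered anywhere. The call-back number is partly covered.

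**Is step 3 clear for this population?** Participants live in the community at least 3 months after stroke and are uninsured or underinsured (4.1). They are not in rehabilitation (4.2), and they are recruited from registries and support groups (4.3). Nothing there implies a physician currently on service for them. The phrase could equally mean the physician on duty at the service that receives the referral. The text does not settle which.

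**Cost of the check.** Assume that confirming location and number takes 1 to 2 minutes. Against the stated 1-hour screen, 1/60 = 1.7% and 2/60 = 3.3%.

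**Frequency.** The documents give neither the number of remote screens nor a rate of positive findings, so expected use is not estimated.

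**The case against.** The plan is far from empty. The Pittsburgh service runs around the clock and directs people to immediate care. A contact person is notified, and steps 1 and 2 can be done by telephone. The suicidality items were included on specialist advice, and the investigators report that the same three steps have served this population for a decade. Silence on how a referral is made is not evidence that it is passive. Evaluators may be clinicians who would stay on the line anyway, and site procedures or consent materials not seen here may hold addresses and instructions.

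Much of this stands, and it rules out several stronger readings that a reader might infer:

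- *The team has no way to call back.* Not supported. The recruitment call in 4.3 means a number will usually exist, and step 2 gives a second route through the contact person.
- *St. Louis and Chicago have no crisis response.* Not supported. Step 1 refers to local services at every site; only the names of those services are missing.
- *Step 3 cannot work because participants have no such physician.* Not supported. The wording is unclear and may mean the receiving service's physician.
- *Evaluators will leave suicidal people unattended.* Not supported. The text does not say that nothing beyond the three steps is done.

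The track record is only a partial answer. The sentence concerns major depressive disorder, does not mention suicidality, and does not say that those studies screened remotely. Procedures outside the documents may fill the gaps, but 6.2.1 cites none.

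**Conclusion.** The point holds in a limited form. Section 6.2.1 uses one refer-and-notify response for two findings of different urgency and contains nothing specific to teleconference. Two elements are absent throughout the documents: confirmation of a remote participant's current location, and, in both modes, a requirement to stay with a suicidal person until a crisis service has taken over. The missing service names for two cities and the ambiguous physician in step 3 are secondary matters of wording.

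The conclusion rests on the text alone and assumes that no unseen site procedure supplies these steps. It has no bearing on the trial's outcomes or analysis. It is a cheap improvement in patient safety that the sponsor should make, held with medium confidence.

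**What to change.** Amend section 6.2.1 as follows.

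(a) Before the mood items in any teleconference screen, explain why, then confirm and record the participant's current location and have the call-back number to hand. If the location is declined, record that and continue.

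(b) If suicidality is found, the evaluator stays on the call, or in the room, until the local crisis service or emergency services has taken over. List the St. Louis and Chicago services beside Pittsburgh's.

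(c) Keep the existing three steps for major depressive disorder without suicidality.

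(d) In step 3, state which physician is meant and add the participant's own physician where there is one. Do not simply replace the step with the usual physician: for an uninsured person who has none, no physician would then be notified.

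The cost is the assumed minute or two per remote screen, a longer visit only when suicidality is found, and one short list of services. No extra staff are needed. The downside is that some people may decline to give their location.
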